## **RTI Health Solutions**

At RTI Health Solutions, as the coordination centre, all key study documents will undergo QC review, senior scientific review, and editorial review. Senior reviewers with expertise in the appropriate subject matter area will provide advice on the design of research study approaches and the conduct of the study and will review results, reports, and other key study documents. All key study documents, such as the analysis plan and study reports, will undergo QC review, senior scientific review, and editorial review. Procedures will be consistent with the International Society for Pharmacoepidemiology (ISPE) *Guidelines for Good Pharmacoepidemiology Practices (GPP)* (ISPE 2015). A quality assurance audit of this study may be conducted by the Sponsor or the Sponsor’s designees.

## **9.9 Limitations of the Research Methods**

This study is subject to limitations related to both the study design and use of secondary healthcare data.

### **9.9.1 Bias and Confounding**

Misclassification bias can occur when exposure or outcome status are ascertained with error. Exposure identification may be based on pharmacy dispensing records, general practice records, immunisation registers, medical records, or other secondary data sources. Currently, the ability to identify specific COVID-19 vaccine products and dates of vaccination in these data sources is only incompletely understood. It is likely that some subjects vaccinated outside the healthcare system will not be recorded in secondary electronic health records databases; this could occur, for example, if healthcare workers receive the vaccination in the workplace

rather than through usual clinical care. The general direction of misclassification would be that some subjects who appear unexposed actually are exposed. Furthermore, the extent to which vaccine brands and batch numbers/lot numbers will be available in the secondary data sources is unknown. To the degree that vaccination registries are in place that capture immunisation history regardless of care setting, the potential for such misclassification will be ameliorated. Concerns about undetected vaccination are addressed in part through use of the SCRI design, which includes only individuals who are known to be exposed.

Outcome definition relies on the accuracy of codes and algorithms to identify outcomes and the data available in each data source. To reduce the probability of **outcome misclassification**, this study plans to use the codes and algorithms proposed by ACCESS. These codes and algorithms are based on literature reviews, have been reviewed by epidemiology and medical experts, and have been used in the “Background rates of AESI protocol” (EUPAS37273). If feasible, identification algorithms will be validated in a sample of cases based on manual review of electronic records or chart abstraction conducted by clinicians blinded to COVID-19 vaccine exposure. Bias analyses may be conducted to evaluate the potential effect of misclassification.

This study is potentially subject to **detection bias**, which can occur when knowledge of exposure leads to differential intensity of outcome ascertainment. A vaccinated individual may be more attuned to the possibility of an adverse reaction following vaccination and have a different threshold for seeking medical evaluation of symptoms than someone who is unvaccinated. Physicians who are aware of a subject’s vaccination status may also have a different threshold for evaluating nonspecific findings in the postvaccination period. We suspect that certain outcomes may be more subject to detection bias, particularly those with a more gradual onset or early symptoms that can be nonspecific, such as autoimmune thyroiditis. In contrast, someone with a new-onset seizure nearly always seeks prompt medical attention. Concerns that publicity about potential adverse effects may lead to differential ascertainment over time can be addressed through inspection of IRs in sequential periods during the study.

**Uncertainty about risk periods** may lead to misclassification and potential attenuation of risk estimates in the cohort design, particularly in the SCRI design. For AESIs with gradual onset, such as multiple sclerosis or peripheral neuropathies, the date of disease onset will likely precede the date of first recorded diagnosis; for events diagnosed shortly after vaccination, there is the possibility that the order of events (exposure/outcome) may actually be reversed. These concerns can be partially addressed through sensitivity analyses that introduce lag intervals. Approaches to address this limitation will be discussed in the SAP.

For AESIs with **known risk windows**, the main cohort analysis will pool risk estimates from risk windows after the first and second doses of AZD1222. Under the assumption that the

effect of a first or second dose in both populations is homogeneous, this pooling will increase study size and statistical precision. As this assumption is likely inaccurate, eg, because receiving a first dose sensitises the immune system to react against a second dose, the estimates of the main analysis could be biased. This factor may be especially important when evaluating immune-mediated AESIs, such as anaphylaxis. We will evaluate the IRs after each dose and report the relative effect measures separately.

For AESIs evaluated using SCRI, it is assumed that the occurrence of the event must not censor or affect the observation period, however, if such events are frequently fatal, this may relevantly impact the evaluation. To assess whether this outcome occurs, we will evaluate and report the number of fatal AESI that led to a censoring of the risk interval.

This study plans to estimate the risk of AESIs among subjects who have been vaccinated compared with unvaccinated with similar health conditions. Subjects who do not receive vaccination (or receive it later) may have different health status and patterns of healthcare compared with those who are vaccinated. These differences may include a higher prevalence of frailty or underlying chronic conditions ([Webster-Clark et al 2021](#)) among vaccinees. In studies involving vaccines, special attention should be given to bias related to **healthy vaccinee bias** and **confounding by indication** ([Remschmidt et al 2015](#)). While healthy vaccinee bias refers to the situation in which subjects who have better health conditions are more likely to be vaccinated; thus, confounding by indication may be present if subjects with underlying chronic diseases are more likely to be vaccinated than healthy study subjects. Although both situations could occur in this study, it is more likely that vaccination, at least at the beginning of the study period, will be preferentially directed to subjects with more underlying conditions. To address these potential bias/confounding issues, the current study is designed to first match subjects in the vaccinated cohort with comparators of the same age, sex, and at the same calendar date, and then use PS to adjust for potential confounders, including patterns of prior healthcare use.

It is expected that the subject groups targeted for vaccination will change over the course of the study in all countries. Matching on calendar date and age will address this concern and may also reduce potential confounding due to changing patterns of SARS-CoV-2 infection (including the potential for herd immunity to develop over time) and for changes in healthcare-seeking behaviours that have been observed during the pandemic. Being unvaccinated may also be related to lifestyle choices that are difficult to measure. It is unlikely that the data sources will have information on all potential confounders. Failure to account for variables that are unmeasured (or imperfectly measured) may lead to **residual confounding** ([Webster-Clark et al 2021](#)). To address potential confounding, the SCRI, which automatically adjusts for time-invariant confounders, will be used as a secondary approach, and using only postvaccination control periods will avoid the potential bias that use of prevaccination control periods may introduce, as prevaccination health events may affect the probability of exposure.

However, the SCRI design is not well suited to study outcomes with gradual onset, long latency, or risk periods that are not well known.

It is conceivable that over the study period, as more of the population has received vaccines to prevent COVID-19, the population of potential **concurrent unvaccinated comparators will dwindle** or that people who remain unvaccinated may be systematically different from those who choose to be vaccinated. Additionally, the age restrictions on the use of AZD1222 imposed in the UK, Spain, Italy, or the Netherlands, as in most European countries, may make it difficult to find comparable controls for the cohort study. If such a scenario develops, it is proposed to use the SCRI analysis, which includes only exposed individuals, to evaluate vaccine-AESI associations for outcomes that are suitable for this design (Table 3). In the first year of the current study, the availability of comparators and the duration of their follow-up time have been monitored. The results from analyses for the first and second interim reports confirm that the number of concurrent unvaccinated comparators was appropriate; however, the duration of follow-up was too short to evaluate outcomes with long risk windows. For this reason, the protocol was amended to include an active comparator cohort and a historical comparator cohort.

Inclusion of historical comparators raises concerns over non-comparability. The background rate of AESIs may have changed during the pandemic due to the effects of COVID-19 or because of less intensive ascertainment due to access issues or healthcare-seeking behaviours. Using historical controls from the pandemic era before the availability of COVID-19 vaccines could theoretically overcome this challenge. The current protocol plans to select comparators from 2017-2018 matched on the day and month of the first vaccination of the exposed subjects—an approach that could control for seasonality.

Results from Interim Report 2 also showed that vaccination against COVID-19 occurred within targeted age groups with different COVID-19 vaccines and at different calendar times, and that there was little overlap for some age groups, and when some overlap of age groups occurred, this occurred in different calendar periods. A pre-matching feasibility assessment of cohort comparability will be performed to examine the overlap of matching covariates in the AZD1222 cohort and the **active comparator cohort** (Section 9.7.3.4). Large values of AUC of ROC curves indicate the importance of adjusting for all confounders (observed and unobserved) correctly to prevent unfair treatment comparisons. In the situation of large values of AUC, the suitability of the analysis with the active comparator will be reconsidered. The active comparator analysis will be focused on the two-dose vaccination strategy, which may lead to selection bias, which may or may not be differential.

Since mRNA doses are much closer in time than AZD1222 vaccination doses, events following dose 1 for mRNA vaccinees could fall in the dose 2 risk window. This will be less likely with the dose 2 risk window in the AZD1222 cohort.

**Multiple use of the same comparator:** In the PRAC assessment report for Interim Report 1 (Assessment Report for the Post-Authorisation Measure 007.6, 21 July 2022), the rapporteurs expressed concerns regarding the multiple use of the same concurrent unvaccinated subject based on the matching with replacement in a ratio of 1 AZD1222-vaccinated subject to 5 concurrent unvaccinated subjects. Based on the PRAC's suggestion, the matching ratio for AZD1222 to concurrent unvaccinated subjects was modified from 1:5 to 1:1. This measure reduced the number of times that a concurrent unvaccinated subject was matched. In the analysis for Interim Report 1, the percentage of comparators used only 1 time for matching ranged from 35% in CPRD to 60% in ARS Toscana, while in the analysis for Interim Report 2, it ranged from 65% in CPRD to 85% in ARS Toscana. Similarly, the percentage of comparators used 3 times or more ranged from 18% in ARS Toscana to 46% in CPRD in Interim Report 1, while in Interim Report 2, it ranged from 2% in ARS Toscana to 13% in CPRD (results for Interim Report 2 are preliminary). Robust estimation of the variance will be used to account for the remaining repeated matches to concurrent unvaccinated subjects, as well as to account for the repeated matches when using active comparators or historical comparators. PRAC Rapporteurs also expressed their concern about the use of general estimating equations (GEEs) taking into account only one of the sources of correlation to estimate the variance of the incidence rate ratio of AESIs and proposed the use of GEE methods with the combination of 3 covariance matrixes ([Austin and Cafri 2020](#), [Stuart 2010](#)). The 2 GEE methods together with bootstrapping will be evaluated for their use in the final study report. Bootstrapping may be considered if it is the only way to provide measures of uncertainty given the constraints of study size and issues with convergence.

Finally, data for some of the covariates proposed to define the subgroups of interest included as having missing information in the RMP may not be complete. Patients who are immunocompromised will be identified using several diagnoses of diseases that involve immunosuppression and use of immunosuppressive medications. It is acknowledged that availability of information on immunosuppressive drugs that are given in the hospital or recorded in separate databases will be limited, but whenever possible, this information will be used and ascertainment of the covariates to identify subjects who are immunosuppressed will be complemented using information on diagnosis and procedures. Identification of haematological malignancies will be complemented whenever possible with data from all data available in each data source. Similarly, human immunodeficiency virus (HIV) infection is known to be incompletely recorded in some databases such as the CPRD, where only around 55% to 67% of subjects who are HIV positive have a diagnosis in the primary care database ([Gompels et al 2019](#)). To overcome this limitation, all data available in each data source will be used, including, eg, hospital data (HES) in the CPRD, and data prescriptions or dispensing of anti-retroviral medications that are specific to the disease and expected to be available. Additionally, the identification of women who are pregnant or breastfeeding might be challenging in the selected data sources. To identify pregnancy onset, information on delivery or birth dates, proxies for them (eg, delivery hospital admission date), or other valid methods

will be used for estimation ([Margulis et al 2015](#)). To identify women who are breastfeeding, the mother-baby linkage and other approaches will be used.

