### **Data analysis**

Baseline characteristics of the subjects who received AZD1222 will be described overall and in sequential periods over time. Patterns of use of a second COVID-19 vaccine dose (AZD1222 and others) will be described.

For the cohort study, exposure propensity scores (PS) will be used to refine the balance between study cohorts, which will be matched initially on index date, age, sex, region, prior diagnosis of COVID-19, and status according to each of the 5 special populations, as applicable for each comparator. Propensity scores will be used to control for confounding either by analytic methods involving stratification or weighting. For AESIs with known risk windows, ie, for which the risk interval is characterised, crude IRs and 95% confidence intervals (CIs) for the vaccinated population and for the comparator cohorts will be estimated. Poisson regression models are proposed to estimate crude and adjusted IRRs and IR differences with 95% CIs comparing vaccinated and comparator cohorts. These analyses will combine all person-time at risk after dose 1 and dose 2 (if it was received). Exploratory analyses will report the IRs by specific dose. Comparative analysis between AZD1222 and active comparators will be limited to those with 2 doses of AZD1222 or an mRNA COVID-19 vaccine, and to the risk window after dose 2. For AESIs with unknown risk windows, cumulative incidence will be estimated using Kaplan-Meier methods starting after dose 1. Cox regression models are proposed to estimate crude and adjusted hazard ratios and 95% CIs.

For comparative analysis using the SCRI approach, conditional Poisson regression will be used to estimate IRRs and 95% CIs of specific AESIs with known risk windows, where appropriate.

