## 7. RATIONALE AND BACKGROUND

The novel coronavirus SARS-CoV-2 (severe acute respiratory syndrome coronavirus 2), the cause of coronavirus disease 2019 (COVID-19), has led to a global pandemic. AZD1222 (called Vaxzevria® in Europe) is a vaccine that was developed to prevent COVID-19.

Coronaviruses are enveloped viruses with positive-sense single-stranded RNA genomes. The spike glycoprotein is a coronavirus surface protein involved in receptor binding and mediating

virus entry into host cells during infection (Li 2016). AZD1222 is a recombinant replication-defective chimpanzee adenovirus expressing the SARS-CoV-2 spike glycoprotein. Development of AZD1222 was initiated by the University of Oxford with subsequent transfer of development activities to the Sponsor.

On 30 December 2020, the UK Medicines and Healthcare products Regulatory Agency (MHRA) provided authorisation for emergency supply of AZD1222, and on 29 January 2021, the European Commission granted conditional marketing authorisation for the vaccine. Now known as COVID-19 Vaccine AstraZeneca, the vaccine in both jurisdictions is indicated for active immunisation to prevent COVID-19 caused by SARS-CoV-2, in individuals aged 18 years and older. The vaccination course consists of 2 separate intramuscular injections. The second dose should be administered between 4 and 12 weeks (28 to 84 days) after the first dose. Since May 2022, a booster dose may be given at least 3 months after the second dose. A booster dose of AZD1222 can also be given to adults who have had 2 doses of an authorised mRNA COVID-19 vaccine but is beyond the scope of this study. At the national level, public health bodies may issue official recommendations, taking into account emerging effectiveness data and the limited safety data.

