### Inclusion Criteria

#### AZD1222 Matched Cohort

Subjects in the **AZD1222 matched cohort** will include those subjects in the *all vaccinated first dose population* (ie, received at least 1 dose of AZD1222 within the study period, and this was their first COVID-19 vaccine dose) that fulfil *all* the following inclusion criteria:

- Have at least 12 months of data available before the index date
- Have no record of vaccination with any other COVID-19 vaccine on or before the index date

The **index date** will be the date when a subject receives the first AZD1222 dose within the study period.

For the comparison with the active comparator cohort, only AZD1222 vaccinees with a first and second dose of AZD1222 will be selected. The **index date** for this comparison will be the date of the second dose.

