#### Active Comparators Cohort

Subjects in the active comparator cohort will include those subjects in the *all mRNA vaccinated first dose population* (ie, received at least 1 dose of an mRNA vaccine within the study period, and this was their first COVID-19 vaccine dose) that fulfil *all* the following inclusion criteria:

- Have at least 12 months of data available before the index date
- Have no record of vaccination with any other COVID-19 vaccine on or before the index date

The **index date** is the date when a subject received the first identified Comirnaty dose or the first identified Spikevax dose within the study period.

All subjects in the active comparator cohort will be **matched** to subjects in the AZD1222 vaccinated cohort on index date (by  $\pm 2$  weeks), age ( $\pm 2$  years), sex, region, prior diagnosis of COVID-19, and status according to the 5 special populations. Matching will be done with replacement at a ratio of 1:1. The same matching approach will be used for the comparative analysis with the 2 doses population using as **index date** the date when a subject received the second consecutive dose of Comirnaty or Spikevax within the study period.

Note that the distribution for matching covariates was driven by the vaccination policies that steered mRNA and AZD1222 vaccines into specific age and special population categories that varied over time. Where pre-matching populations are deemed significantly different, the suitability of this analysis will be reconsidered as the ability to make comparative inference on the safety profile is limited to a specific sub-population that may not be representative of the general AZD1222 and active comparator populations. To examine this risk, a pre-matching feasibility assessment of cohort comparability will be performed (see section 9.7.3.4).

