### Exclusion Criteria

The following exclusion criterion will be considered in all the cohorts:

[figure not shown]
- For each AESI, subjects (in any matched cohort) who had a specific AESI (Table 3) during the look-back period before the index date will be excluded from the cohort for the analysis of that specific AESI, but not from the cohorts for analysis of other AESIs.
  - If a subject had a specific AESI between the index date and the start of the risk window or had any censoring criteria within this time period, the subject will be excluded from the analysis of that specific AESI.

The number of subjects in the *all AZD1222 vaccinated first dose population* and in the *all mRNA vaccinated first dose population* excluded because they had no matches will be described. Similarly, the number of subjects in the initial pool of potential concurrent

unvaccinated comparators and historical comparators that fulfil the inclusion criteria but are excluded because they had no matches will be described.

In the analysis of a specific AESI, if a subject in the *AZD1222 matched cohort* is excluded due to having a prior history of that specific AESI, all its matched subjects will also be excluded from that analysis. Analogously, if the matched subject in the *concurrent unvaccinated comparator* matched cohort or in the *active comparator* matched cohort or in the *historical comparator* matched cohort is excluded, then the corresponding subject in the *AZD1222 matched cohort* will also be excluded from the analysis of that specific AESI.

**Figure 2** Assembly of Study Cohorts

[figure not shown]

Note: The process illustrated here will be conducted separately in each data source. Index date refers to the date of the first dose of AZD1222 for each vaccinee and for each unvaccinated comparator subject (minus 3 or 4 years for each matched historical control) or the date of the first dose of an mRNA vaccine for each active comparator subject. Subjects in the concurrent unvaccinated cohort will be allowed to enter the AZD1222 or the active comparator cohort if they later fulfil specific cohort entry criteria.

Note that the comparative analysis between AZD1222 and active comparator cohorts will be conducted among vaccinees who have received 2 doses. COVID-19, coronavirus disease 2019; SCRI, self-controlled risk interval.

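### In the two-dose AZD1222 versus mRNA comparison, unequal carry-over of dose-1 risk into the dose-2 window can shift the IRR, and no planned analysis shows by how much

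*Protocol*

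**What the plan says.** The Abstract (Data analysis) says that the comparison with active comparators is "limited to those with 2 doses of AZD1222 or an mRNA COVID-19 vaccine, and to the risk window after dose 2". Section 9.2.1.1.3 sets the start of follow-up to match. The AZD1222 index date "for this comparison will be the date of the second dose", and the mRNA index date is "the date when a subject received the second consecutive dose of Comirnaty or Spikevax within the study period". Under Exclusion Criteria, subjects "who had a specific AESI (Table 3) during the look-back period before the index date will be excluded from the cohort" for that AESI.

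Table 3 gives many AESIs a window of 1-42 days and a clean look-back of 365 days, for example Guillain-Barré syndrome (GBS), Bell's palsy, myocarditis/pericarditis and TTS. Other known windows run to 14, 28 or 90 days.

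For AZD1222, section 7 states: "The second dose should be administered between 4 and 12 weeks (28 to 84 days) after the first dose". For the mRNA vaccines the protocol gives no interval, only that their doses come much closer together. On that ground section 9.9.1 concedes that "events following dose 1 for mRNA vaccinees could fall in the dose 2 risk window", and adds that this is less likely for AZD1222. It gives no direction, size or remedy.

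**The concern.** An AESI caused by dose 1 is treated according to when dose 2 was given. If it occurs before dose 2, the subject is excluded at baseline. If it occurs after dose 2, it counts as a dose-2 event. With a shorter dose interval, more of the dose-1 risk window lies inside the counted time. Under a common 42-day window, the mRNA arm can therefore collect late dose-1 events of a kind that the AZD1222 arm has mostly removed.

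The IRR would then be neither a clean comparison of second doses nor a comparison of two-dose courses, since a course comparison would count the events between doses. The shift is systematic, so more data would not shrink it.

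Section 8 presents the two-dose restriction as a more robust way to handle differences in timing by vaccine and by dose. The restriction does not deal with this overlap.

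**Working it through.** **The plan's own figure.** The only figures for this comparison are the precision values in Table 6. For GBS the inputs are 2 per 100,000 person-years, 5 million per arm, 84 days and a true IRR of 1. Expected events per arm are 5,000,000 × 84/365.25 × 0.00002 = 23.0. SE = √(2/23.0) = 0.295. P(upper limit < 3.0) = Φ(ln 3/0.295 − 1.96) = 0.96, as stated. The protocol gives no figure for carry-over.

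**Inputs for carry-over**
- Window L = 42 days; look-back 365 days (Table 3).
- AZD1222 interval: 28 to 84 days (section 7).
- mRNA interval: not in the protocol; assumed 21 to 28 days.
- Dose-1 rate ratio r, flat over days 1-42: not in the protocol; assumed 1.5 or 2.
- No effect of either second dose.

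**Formula.** With interval g, the dose-2 window covers days g+1 to g+L after dose 1. The share of it inside the dose-1 window is c = max(0, L − g)/L. The rate in that window, relative to background, is 1 + (r − 1)c. The expected IRR is the AZD1222 value divided by the mRNA value.

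**Shares**
- mRNA: g = 21 gives 21/42 = 0.50; g = 28 gives 14/42 = 0.33.
- AZD1222: g ≥ 42 gives 0; g = 28 gives 0.33.
- AZD1222 uniform over the 57 whole days from 28 to 84: (14 + 13 + … + 1)/42/57 = 105/42/57 = 0.044.

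**Expected IRR, same r for both vaccines**

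| AZD1222 interval | r | mRNA 21 d | mRNA 28 d |
|---|---|---|---|
| 42 d or more | 2 | 1/1.5 = 0.67 | 1/1.333 = 0.75 |
| uniform 28-84 d | 2 | 1.044/1.5 = 0.70 | 1.044/1.333 = 0.78 |
| 28 d | 2 | 1.333/1.5 = 0.89 | 1.333/1.333 = 1.00 |
| 42 d or more | 1.5 | 1/1.25 = 0.80 | 1/1.167 = 0.86 |

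A day-by-day life table that removes events before dose 2 gives the same values where it was run (0.667 and 0.889 for mRNA at 21 days, r = 2). For GBS with 5 million per arm, r = 2, mRNA at 21 days and AZD1222 at 42 days or more, the expected counts are 11.5 AZD1222 events and 11.5 × 1.5 = 17.2 mRNA events.

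**Where the shift weakens, vanishes or reverses**
- r = 1 in both arms: IRR 1.00. Background events are handled alike.
- Front-loaded excess: if r = 2 holds only for days 1-28, mRNA at 21 days carries over 7 of 42 days and the IRR is 1/1.167 = 0.86. At 28 days it is 1.00.
- AZD1222 r = 2 at 28 days with mRNA r = 1: IRR 1.333/1 = 1.33, against AZD1222.
- Windows of 14 days or less: no overlap at a 21-day interval. A 28-day window at 21 days has c = 7/28 = 0.25, so r = 2 gives 1/1.25 = 0.80.

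**Planned analyses.** Section 9.7.10 covers COVID-19 censoring, pair censoring, alternative windows and definitions for TTS, an alternative window for thrombocytopaenia with bleeding, validated TTS cases and hospital data. The alternative windows all start at day 1 and are cut at the far end, so they keep the days where the overlap lies. For self-controlled analyses, section 9.2.3.2 joins the risk periods when dose 2 falls inside the dose-1 window. The active-comparator analysis has no such rule.

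**The case against.** The strongest reply is that the limitation is disclosed and little hangs on it. Section 9.9.1 names the asymmetry and the arm more affected. The objective is exploratory, no hypothesis is tested, and the feasibility assessment in section 9.7.3.4 may stop the comparison. Section 9.7 commits to weighing possible bias, section 9.7.2 will describe dose intervals for both vaccines, and the dose-specific rates in section 9.7.6 may show whether a dose-1 excess exists. This limits the weight of the point. It does not answer it: the feasibility assessment looks at matching covariates, not at which dose an event is attributed to, and no planned step estimates the carry-over.

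The reply is also right about size. The mRNA interval and the dose-1 ratio are assumptions, and a flat 42-day excess is not neutral. For TTS, section 9.5 itself notes that onset appears to fall within 4 weeks.

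A reader might infer that the design makes AZD1222 look safer, or that all AZD1222 dose-1 cases are removed. The protocol supports neither as a general statement. The first needs an mRNA dose-1 excess lasting past dose 2, and the direction can reverse. The second holds for a 42-day window only at intervals of 42 days or more; at 28 to 41 days, up to 14 late dose-1 days are counted for AZD1222 too.

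**Conclusion.** The point holds conditionally. The index date, the dose-2 window, the look-back exclusion and the difference in dose spacing together create unequal dose-1 carry-over. It biases the IRR if dose 1 raises the AESI rate and the excess extends beyond dose 2.

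Under the stated assumptions (42-day window, mRNA interval 21 to 28 days, flat ratio of 2 for both vaccines, no dose-2 effect), the expected IRR runs from 0.67 to 1.00, depending on the AZD1222 interval. It is 0.70 to 0.78 if those intervals are spread evenly over 28 to 84 days. A front-loaded excess brings it closer to 1. Without a dose-1 excess it is 1. A risk confined to AZD1222 dose 1 at short intervals takes it above 1.

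A reader might go further and treat any ratio below 1 as spurious unless a restricted analysis agrees. That is not warranted: the restricted analysis is imprecise and covers a different period, so a real early dose-2 difference could fail it. In an exploratory comparison with the asymmetry already disclosed, this is a cheap improvement, not a defect that invalidates the analysis.

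**What to change.** Add one sensitivity analysis to section 9.7.10, for the active comparator only. Limit it to known-window AESIs whose window is longer than the observed dose interval, such as the 1-28, 1-42 and 1-90 day windows. In both members of each pair, count only the dose-2 window days beyond the end of the dose-1 window in both members. With a 42-day window and a shorter interval of 21 days, these are days 22-42 after dose 2. Under no dose-2 effect, and with the dose-1 excess confined to its window, the expected IRR returns to 1.00 for any r.

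Report it beside the main estimate, and state in section 9.9.1 that the main IRR may include unequal dose-1 carry-over in either direction.

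The dates are already held, so the cost is one extra run and reduced precision. At a 21-day interval, a 42-day window keeps 21 of its 42 days. For GBS with 5 million per arm, expected events fall from 11.5 to 5,000,000 × 21/365.25 × 0.00002 = 5.7 per arm. SE = √(2/5.75) = 0.59, so P(upper limit < 3.0) is about 0.46, against 0.75 for the full 42-day dose-2 window. A 90-day window keeps only days 70-90. The first weeks after dose 2 are not seen, so the analysis supplements the main result and should not gate it.
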